### **3.4. Endpoints**

#### **Primary:**

- The percentage of evaluable patients with an improvement in the Mayo Classification.

Mayo Classification;

- Level 0: thrombus limited to the renal vein
- Level 1: into IVC  $< 2cm$  from renal vein ostium level
- Level 2: IVC extension  $> 2cm$  from renal vein ostium and below hepatic vein
- Level 3: thrombus at the level of or above the hepatic veins but below the diaphragm
- Level 4: thrombus extending above the diaphragm.

#### **Secondary:**

- % change in surgical approach
- % change in VTT height
- Radiological response (RECIST)
- Evaluation of morbidity assessed by Clavian-Dindo classification

### **Primary Safety Endpoints**

Thirteen patients will be recruited at first; if at least 1 patient has an improvement in the Mayo classification a further 7 patients would be recruited (to the final total of 20 patients who have received study drug), to receive study drug. At least 3 patients showing reductions in Mayo score are required for a positive trial. The early stopping rules are:

- (1) If a single M0 patient progresses to the point where surgery is no longer possible, then recruitment of new patients will be suspended following a review by the data monitoring committee (DMC).
- (2) If a single M0 patient becomes M1 recruitment of new patients will be suspended following a review by the DMC.
- (3) If in 3 patients the VTT extends but patients remain surgically resectable the trial will close. If the VTT has extended the patient will be expedited and operated on as soon as possible.

Where there is diagnostic doubt at site, the week 3 MRI abdomen scans (and CT chest for M0 patients) a central review will be conducted to determine if a patient has progressed as per RECIST 1.1 criteria. In addition those particular patient cases will be discussed on an individual basis by the trial steering committee (TSC).

The central review for final analysis will be conducted by radiologists based at Addenbrooke's Hospital.

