### **11.2. Data Monitoring and Ethics Committee**

An independent Data Monitoring Committee (DMC) will be established and will meet 6 monthly in the first instance and annually thereafter (and at any other time at the committee's discretion). There will be an extra meeting of the committee after 13 patients have been recruited. None of the committee members will be involved in the trial. The committee will receive regular reports from SCTR. It will submit its comments and recommendations to the Trial Steering Committee and Trial Management Group (TMG).

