### **11.3. Trial Steering Committee**

A trial steering committee will be established to provide overall supervision of the trial, in particular; trial progress, adherence to protocol, patient safety, and consideration of new information. The committee will meet 3 monthly in the first instance and then 6 monthly thereafter. The committee will then meet 3 monthly during close out/ final analysis.

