approvals and authorisations have been obtained from the independent research ethics committee, and NHS Research and Development departments (R&D). The Trial Steering Committee (TSC), including members of the research team and an radiologist, oncologist, statistician, and lay members, will be responsible for the progress and conduct of the study and convene annually. A Trial Management Group will meet quarterly. A Data Monitoring and Ethics Committee (DMC) will convene 6 monthly, to review all data including adverse events and review the stopping policy for the trial, if necessary. Specific issues that will be looked at include: tolerability of initial dose, dose reductions, toxicities (including interaction of the mild increased bleeding risk), imaging & review schedules.

**Laboratories** – Accredited local laboratories shall be used for all on-study tests. Samples from the translational research will be transferred to a central laboratory based at the University of Cambridge. The details of the sampling, storage and shipping protocols are covered in appendix 6 and the NAXIVA laboratory manual in accordance with all prevailing regulatory requirements.

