5.2 Early stopping rules

Patient safety will be ensured by applying the following early stopping rules:

- (1) If a single M0 (staging data: cancer has not spread to other parts of the body) patient progresses to the point where surgery is no longer possible, then recruitment of new patients will be suspended following a review by the data monitoring committee (DMC)
- (2) If a single M0 (staging data: cancer has not spread to other parts of the body) patient becomes a M1 (staging data: cancer has spread to other parts of the body) patient, recruitment of new patients will be suspended following a review by the DMC.
- (3) If in 3 patients the VTT extends (as indicated by an increase in Mayo classification) but patients remain surgically resectable the trial will close. If the VTT has extended the patient will be expedited and operated on as soon as possible.

6 Efficacy evaluations

Note that these evaluations will be made for both the evaluable and ITT populations. This represents a sensitivity analysis that assesses whether results are robust in the ITT population.

This study will use the following efficacy parameters:

- At least 3 evaluable patients showing improvement in disease extent between screening and week 9 are required for a positive trial.
- The change in Mayo classification between screening and week 9 in evaluable patients will be presented with the percentage of patients with an improvement, no change and a deterioration in Mayo classification shown. Percentages will be calculated using both the evaluable population and the ITT population.
- The VTT length measurement will be calculated as the sum of: (1) length of IVC tumour thrombus ABOVE renal vein (measured from ostium of RV+IVC to tip of tumour thrombus); (2) length of IVC tumour thrombus BELOW renal vein (measured from ostium of RV+IVC to tip of tumour thrombus) and (3) length of RV thrombus. Those patients who are identified as “main renal vein” will only have the third value populated. Any values that are missing cannot be assumed to represent 0 and must be clarified either via contact with sites or by manual checking of the paper CRF.

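### Safety rules 1 and 2 suspend recruitment only after a DMC review that has no deadline, no interim hold and no duty to notify, and SAP 3.1.2 states a different consequence and timing

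*Protocol*

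**What the plan says.** Protocol 3.4 (Primary Safety Endpoints) has three early stopping rules. Rule 1 covers an M0 patient who progresses until surgery is no longer possible: "then recruitment of new patients will be suspended following a review by the data monitoring committee (DMC". Rule 2 reads "If a single M0 patient becomes M1 recruitment of new patients will be suspended following a review by the DMC". SAP 5.2 repeats both with the same order of events ("recruitment of new patients will be suspended following a review by the DMC") and adds no time limit. Rule 3, three patients whose thrombus extends but who remain resectable, closes the trial without a DMC step. The Interim Analysis text in Protocol 9.2 applies rule 3 at any time in the study.

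SAP 3.1.2 treats the same rules differently. It places their assessment in the interim analysis, subject to adequate data, which it explains as complete data for thirteen patients. It says the trial is stopped if any rule is breached.

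On meetings, Protocol 11.2 says the DMC "will meet 6 monthly in the first instance and annually thereafter (and at any other time at the" committee's discretion, and it adds one meeting after 13 patients have been recruited. Protocol 13 says "A Data Monitoring and Ethics Committee (DMC) will convene 6 monthly" and mentions no later change to annual.

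**The concern.** Rules 1 and 2 are written to act on a single event, and Protocol 1.5 names these same outcomes (operable to inoperable, non-metastatic to metastatic) as risks of the 8-week treatment period. Yet as worded, recruitment stays open until the DMC has reviewed the case, and nothing says when that must be or who sets it in motion. A site and trials unit that follow the text exactly could go on enrolling after an event that was meant to halt enrolment. Those enrolled could include M0 patients, who under the inclusion criteria have a primary tumour considered resectable at entry.

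The SAP adds a second uncertainty. A reader cannot tell whether a breach suspends recruitment after a DMC review or stops the trial, or whether the rules operate continuously or are assessed at the interim.

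**Working it through.** **The plan's own design figure.** Protocol 9.1 gives 13 + 7 = 20 patients, continuing with at least 1 improvement and succeeding with at least 3. The chance of success is the sum over x = 1 to 13 of P(X₁ = x) × P(X₂ ≥ 3 − x), with X₁ ~ Bin(13, p) and X₂ ~ Bin(7, p). At p = 0.05 this is 0.0736 (limit 0.10). At p = 0.25 it is 0.903 (stated 90%). The design reproduces and is not in dispute. It supplies the cap of 20 and the meeting point at 13.

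**Accrual.** Protocol 9.1 plans 20 patients in 24 months: 20/24 = 0.833 a month. The thirteenth patient is expected at 13/0.833 = month 15.6.

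**Enrolment after a trigger event.** Expected number = 0.833 × months to review. The documents do not give the delay, so it is an assumption, shown as a range. Accrual is taken as steady (Poisson). For routine meetings the event is taken as equally likely at any time in the interval, so the mean wait is half the interval.

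| Assumed timing of review | Mean wait (months) | Expected further patients |
|---|---|---|
| Suspension on notification | 0 | 0 |
| Called within 2 weeks | 0.5 | 0.4 |
| Called within about 4 weeks | 1 | 0.8 |
| Next 6-monthly meeting | 3 | 2.5 |
| Next annual meeting | 6 | 5 |

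For the two short delays, the chance of at least one further entry is 1 − exp(−λ), where λ is the expected number: 34% at 2 weeks and 57% at one month. For routine meetings, let L be the expected accrual over a full interval (5 or 10). The chance of at least two further entries is 1 − [2 − (2 + L)exp(−L)]/L, which is 61% for 6-monthly and 80% for annual meetings.

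**What lowers the routine-meeting figures.** A full 12-month gap before the extra meeting needs the annual phase to begin by month 15.6 − 12 = 3.6 of recruitment. After that meeting only 20 − 13 = 7 patients remain. Counting DMC meetings from the start of recruitment:

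- 6-monthly phase lasting to month 6: longest gap 15.6 − 6 = 9.6 months, or 8 patients over the full gap and 4 on average.
- 6-monthly phase lasting to month 12: longest gap 24 − 15.6 = 8.4 months, or 7 patients and 3.5 on average.

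**The rule texts side by side.**

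| | Protocol 3.4 and SAP 5.2 | SAP 3.1.2 |
|---|---|---|
| Consequence of rule 1 or 2 | Recruitment suspended after DMC review | Trial stopped |
| When assessed | On a single event, no time limit | At the interim, on complete data for thirteen patients |

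At planned pace the second timing cannot fall before month 15.6.

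**Reporting routes.** Protocol 7.1 does not list progression to inoperable or M1 disease as an SAE. Protocol 7.2 records only related reactions. Protocol 7.3 sends SAE reports to the trials unit within 24 hours and then to the Chief Investigator, with no onward step to the DMC. Protocol 11.2 gives the DMC regular reports of unstated frequency.

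**The case against.** **The review may be meant as event-driven.** The rules are triggered by one patient, and Protocol 11.2 lets the DMC meet whenever it chooses. On that reading the routine interval does not set the delay, and the smaller figures apply. This stands, and is why the size is given as a range. It does not close the gap: the power to meet is discretionary, and the committee cannot use it for an event that nobody is required to report to it.

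**Existing routes may carry the news.** An investigator may class such an event as medically significant and report it as an SAE within 24 hours, and under Protocol 13 the Trial Management Group meets quarterly. That makes prompt notice plausible, but it depends on judgement and is not a stated duty.

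**Review first may be deliberate.** One apparent progression may need confirming before a small trial is halted. That is a fair reason for the DMC to decide what happens next. It does not explain why enrolment should stay open in the meantime without limit.

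**SAP 3.1.2 may describe only an extra checkpoint at the interim.** That is possible, but the SAP does not say so, and stopping the trial would still differ from suspending recruitment.

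**Steering committee intervals.** Protocol 11.3 ("The committee will meet 3 monthly in the first instance and then 6 monthly thereafter") conflicts with Protocol 13 ("will be responsible for the progress and conduct of the study and convene annually"), and a reader might infer that this too delays suspension. The documents do not support that. The steering committee has no part in suspension under rules 1 and 2, and its discussion of individual doubtful cases is not tied to scheduled meetings. The conflict is clerical.

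**Conclusion.** The point holds as a gap in wording and a conflict between passages. Rules 1 and 2 put suspension after a review with no deadline, no interim hold and no duty to notify the DMC. SAP 3.1.2 disagrees with them on consequence and timing, and Protocol 11.2 and 13 disagree on DMC frequency after the first period.

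The size depends on an assumed delay: about 0.4 to 0.8 further patients if the review is called within 2 to 4 weeks, and about 2.5 or 5 on average if it waits for a 6-monthly or annual meeting. The last two come before the cap, the extra meeting and any discretionary meeting reduce them. All counts are for M0 and M1 patients together. The documents give no split, so the number of M0 patients affected is unknown and lower if any M1 patients enter.

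A reader might multiply accrual by the full meeting intervals and infer that 5 to 10 patients, a quarter to half of the trial, would enter after a trigger. The documents do not support that as the expected size. Nothing ties the review to a routine meeting, those are full-interval figures, and 10 needs a 12-month gap that the meeting after 13 patients and the cap of 20 largely rule out.

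**What to change.** 1. In Protocol 3.4 and SAP 5.2, reword rules 1 and 2 so that recruitment is suspended on notification of the event, pending DMC review. The DMC still decides whether it reopens.
2. Make the rule 1 and rule 2 events notifiable to the trials unit by the existing 24-hour route in Protocol 7.3, and state that the unit passes them on to the DMC.
3. Reconcile SAP 3.1.2 with Protocol 3.4 and SAP 5.2 on both consequence (trial stopped or recruitment suspended) and timing (on the event or at the interim). Changing 3.4 and 5.2 alone would leave the SAP contradicting itself.
4. State one DMC interval in Protocol 11.2 and 13. The steering committee interval in 11.3 and 13 can be tidied at the same time.

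The cost is a wording amendment to both documents, an occasional short pause in recruitment and an ad hoc DMC call. The sample size and the analysis of the primary endpoint do not change.

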Patients having biopsy proven ccRCC will be included in this study, as this is histological subtype of RCC shown to have a benefit from axitinib therapy. Patients with VTT confined to the renal vein (cT3a) will be included as they would benefit from a reduction in the extent of the VTT, regressing from the renal vein back into the kidney, as this would allow curative surgery by laparoscopic rather than more morbid open surgical approaches. Patients with more extensive IVC VTT (infrahepatic, intrahepatic or atrial) will be included, as for patients in each of these groups reducing the extent of the thrombus i.e. from intrahepatic to infrahepatic would potentially reduce extent of surgery and the associated surgical morbidity. Both non-metastatic and metastatic patients will be eligible for recruitment as both groups of patients are likely to benefit, in terms of reduction of level of VTT and surgical morbidity, if axitinib shows efficacy in this patient cohort. It is accepted that there may be different biological processes at play in these 2 cohorts. However, this will be further explored in a fully powered phase 3 randomised control trial, if this phase 2 trial is positive.

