### 3.2. Inclusion Criteria

1. Age  $\geq$  18.
2. Histologically proven clear cell RCC.
3. Immediate resection of the primary tumour considered technically possible.

4. Suitable for and willing to undergo nephrectomy (either cytoreductive or with curative intent)
5. cT3b, cT3c, cT3a (main renal vein)
6. N0, N1, or Nx
7. M0, or M1
8. ECOG performance status 0 – 1
9. Urinalysis  $<2+$  protein. If dipstick is  $\geq 2+$  then a 24-hour urine collection should be performed and the patient may enter NAXIVA only if urinary protein is  $<2$ g per 24 hours.
10. All female patients with reproductive potential must have a negative serum or urine pregnancy test within a maximum of 14 days prior to starting trial treatment.

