#### **Interim Analysis**

An interim analysis will be performed after thirteen patients have been recruited. If no patients have show an improvement in their Mayo classification the trial will be stopped for futility. If at any point in the study 3 patients have a progression of their thrombus (increase in Mayo classification) but remain surgically resectable the trial will be stopped. (Probability of seeing 3 or more progressions if true progression rate <5% is <7.5%). There is no formal stopping rule for efficacy.

The primary analysis will be made on the “treated” population, with patients being included in the analysis only if they have received at least one dose of the drug. In order to assess the impact of any biases an analysis of the “intention to treat” population will also be carried out.

This will include all patients who are registered as eligible for the trial, regardless of whether or not the subsequently received study medication.

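### Stopping rule 3 counts a thrombus extension that is still resectable but not one that has made an M1 patient unresectable, and no other rule covers that patient

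*Protocol*

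**What the plan says.** Protocol 3.4 (Primary Safety Endpoints) sets three early stopping rules.

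- Rule 1 begins "If a single M0 patient progresses to the point where surgery is no longer possible"; recruitment is then suspended following a review by the Data Monitoring Committee (DMC).
- Rule 2 has the same consequence and applies when one M0 patient becomes M1.
- Rule 3 has no M-stage limit: "If in 3 patients the VTT extends but patients remain surgically resectable the trial will close". It adds that "If the VTT has extended the patient will be expedited and operated on as soon as possible".

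Protocol 9.2 (Interim Analysis) defines extension as an increase in Mayo level and keeps the condition: the trial stops if three patients "have a progression of their thrombus (increase in Mayo classification) but remain surgically resectable the trial will be stopped". It supports the rule with the statement "Probability of seeing 3 or more progressions if true progression rate <5% is <7.5" per cent. SAP 5.2 also keeps the condition ("but patients remain surgically resectable the trial will close"). SAP 3.1.2 says that each rule is assessed and that the trial stops if any is violated.

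M1 patients are eligible (Protocol 3.2). Every patient must be operable at entry: "Immediate resection of the primary tumour considered technically possible". Loss of resectability is therefore an on-study event.

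**The concern.** Losing operability is a worse outcome than an extension that can still be resected, yet for M1 patients rule 3 counts the second and leaves out the first. Protocol 1.5 names progression from operable to non-operable as a risk of the treatment period and does not confine it to M0 patients. Nothing in either document gives a reason to leave such a case out of the count of three.

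The consequence shows in one comparison. Three resectable extensions close the trial. Two resectable extensions plus one M1 extension that is unresectable when first seen leave every written rule unmet.

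The gap is narrow. An M0 patient who becomes inoperable meets rule 1 alone. An M1 patient seen as extended but resectable on the week 3 MRI has already been counted before any later loss of resectability. A single-patient trigger for M0 patients only is a defensible choice and is not questioned here.

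**Working it through.** **Rule by rule**

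| Patient | Rule 1 | Rule 2 | Rule 3 |
|---|---|---|---|
| M0, Mayo rise, unresectable | met | – | not counted |
| M0 or M1, Mayo rise, resectable | no | – | counts as 1 of 3 |
| M1, Mayo rise, unresectable when first assessed | no (M0 only) | no (already M1) | no (not resectable) |

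(Rule 2 concerns new metastasis in M0 patients and is not at issue.)

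**The plan's own figure.** With 20 patients and a 5% progression rate, the exact binomial gives P(X ≥ 3) = 1 − (0.3585 + 0.3774 + 0.1887) = 0.0755. The stated 7.5% is thus reproduced to rounding when every progression is counted; at exactly 5% the value is 7.55%, marginally above the stated bound. With the resectability condition applied, the counted rate is 0.05(1 − u), where u is the unresectable share of extensions:

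| u | Rule 3 met, as worded, at a 5% extension rate |
|---|---|
| 0.05 | 6.7% |
| 0.10 | 5.9% |
| 0.25 | 3.7% |
| 0.50 | 1.3% |

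**Effect on the rules taken together.** The documents give no M1 share, no extension rate on axitinib and no unresectable share, so the following are assumptions: n = 20; extension rate e = 5%, 10% or 20%; M1 share m = 0.3 or 0.5; u = 0.05, 0.10, 0.25 or 0.50, the same in M0 and M1; and w, the share of unresectable M1 extensions already counted at week 3 while resectable. Rule 2 is not modelled. Per patient:

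- a = e(1 − m)u: meets rule 1
- b = e(1 − u) + e·m·u·w: counts in rule 3
- c = e·m·u(1 − w): counts nowhere

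P(rule 1 or rule 3 met) = 1 − Σₖ₌₀..₂ C(20,k) bᵏ (1 − a − b)²⁰⁻ᵏ. With every extension counted, b is replaced by b + c.

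Worked case, e = 0.10, m = 0.5, u = 0.10, w = 0: a = 0.005, b = 0.090, c = 0.005.

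- As written: 1 − (0.1358 + 0.2701 + 0.2552) = 33.9%.
- Every extension counted: 1 − (0.1216 + 0.2567 + 0.2574) = 36.4%.
- Gain: 2.6 points.

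Over the whole grid with w = 0:

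| e | As written | Every extension counted | Gain (points) | Gain at u = 0.05–0.10 |
|---|---|---|---|---|
| 5% | 9.0–30.7% | 9.4–31.7% | 0.2–2.0 | 0.2–0.8 |
| 10% | 33.0–55.0% | 34.4–58.2% | 0.8–7.0 | 0.8–2.6 |
| 20% | 76.7–85.2% | 80.2–89.3% | 0.9–10.0 | 0.9–2.9 |

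Setting w = 0 makes these gains upper bounds. With w = 0.5 they fall to 0.1–1.1, 0.4–3.8 and 0.4–4.7 points.

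**The case against.** The strongest reply is that the event is rare and visible. It needs an M1 patient, a Mayo rise, loss of resectability, and no earlier resectable extension at week 3. At a 5% extension rate, 30–50% M1 and u = 0.05–0.10, the expected number is 20 × 0.05 × m × u, or 0.015 to 0.05 patients per trial. A low u may be the realistic end, since Protocol 1.5 states "Patients with more extensive IVC VTT (infrahepatic, intrahepatic or atrial) will be included" and so treats high thrombus as operable. SAP 7.5.1 and 7.5.3 list missed surgery and all extensions, and Protocol 13 lets the DMC review the stopping policy. All of this stands and limits the weight of the point. It does not supply a trigger.

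A second reply is that rule 3 was obviously meant to include worse outcomes, as the probability in Protocol 9.2 suggests by counting all progressions. That may well have been the intent. But the condition appears in all three statements of the rule, and SAP 3.1.2 applies the rules as written. It is also fair to say that the bound in 9.2 is not breached by the current wording (1.3–6.7% at a 5% rate). It simply describes a different rule.

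A third reply is that deleting the condition also brings unresectable M0 extensions into rule 3, whose consequence is closure, whereas rule 1 leads to suspension following DMC review. This is true, and it raises the chance of closure by more than the combined figures show. Those extensions are nevertheless worse than the resectable ones already counted. Wording limited to M1 patients would also close the gap, but rule 3 would then still count only some progressions and would not match 9.2.

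Finally, an M1 patient who becomes inoperable without a Mayo rise would still meet no rule. That case lies outside what rule 3 measures and can stay with the DMC.

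**Conclusion.** The concern holds on the text of both documents. For M1 patients, rule 3 counts the lesser harm and omits the greater one, and neither of the other rules fills the gap. The rule-by-rule result needs no numerical assumption.

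The size does depend on assumptions, and it is modest. If u is 5–10%, the gain in the chance that rule 1 or rule 3 is met is under 3 points at every extension rate examined. The larger gains of 7 to 10 points need half the patients to be M1, half of all extensions to be unresectable, and none of them to have been counted at week 3. The documents support none of these specifically.

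This is a minor wording correction to a safety rule. It does not affect the two-stage design or the primary-endpoint inference.

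**What to change.** In Protocol 3.4, Protocol 9.2 and SAP 5.2, delete from rule 3 the clause that makes continued resectability a condition, and carry the Mayo-increase definition into 3.4. The rule then closes the trial once three patients have had an on-treatment increase in Mayo level, whatever their M status or resectability. Keep rule 1 as the single-patient trigger for M0, and keep the instruction to expedite surgery. In 9.2, give the probability as about 7.5% at a 5% rate, because the exact value is 7.55%.

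The cost is one deleted phrase in three places, with no new data, visits or listings. The downside is a higher chance of closure. At a 5% total extension rate, rule 3 alone would be met in 7.5% of trials instead of 1.3–6.7%, a rise of 0.9 to 6.2 points as u goes from 5% to 50%. The resulting 7.5% is the risk that Protocol 9.2 already accepts.
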